- 16) If the subject develops a Grade 3 solicited injection site or systemic AE (see [Table 9.1](#) and [Table 9.2](#)), develop significant change in arm circumference (increased  $\geq 50$  mm from pre-vaccination measurement at baseline), or ELS which occur during the 7-day period after vaccination, the subject or subject's parent/guardian is required to contact the site immediately. The site staff must attempt for the subject to be seen at the study site within 24 hours to assess the extent of the reaction. In cases of Grade 3 injection site swelling or ELS, the subject (or parent/guardian) is to be instructed to take measurements of the vaccinated arm circumference, and record in the DC, until the swelling is resolved (See Operating Guidelines [OG] for details).
- 17) Set up an appointment for V02 (D30–D44) and instruct the subject or subject's parent/guardian to bring the DC to the visit to discuss the information entered with the study personnel.

*Note: For subjects in the CMI subset, the V02 window will be between D30 and D37*

- 18) Remind the subject or subject's parent/guardian to notify the site in case of an SAE.
- 19) Complete the relevant case report form (eCRF) pages for this visit.

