### 9.3.1.3.2 Reactogenicity (Solicited Reactions From Day 0 to Day 7 After Vaccination)

After vaccination, subjects or subjects' parents/guardians will be provided with a safety DC, a digital thermometer, measuring tape and a flexible ruler, and will be instructed how to use them. The following items will be recorded by the subjects in the DC on the day of vaccination and for the next 7 days (i.e., D0 to D7) until resolution:

- Daily temperature, with the route by which it was taken
- Daily measurement or intensity grade of all other solicited injection site and systemic reactions
- Action taken for each event, if any (e.g., medication)

The action taken by the subject or the subject's parents/guardians to treat any **solicited reactions** will be classified in the eCRF using the following scale:

- 0: None
- 1: Medication (self-medication with an existing prescription or over-the-counter medication)
- 2: Health care provider contact (no new medication prescribed)
- 3: Health care provider contact and prescription of a new medication (health care provider instructed subject to take a new medication, either an over-the-counter medication or one requiring a written prescription)
- 4: Hospitalization (inpatient)

Subjects or subjects' parents/guardians will be contacted by telephone 8 days after vaccination to identify the occurrence of any SAE, Grade 3 solicited adverse reactions (including ELS) not yet reported and to remind them to record all safety information in the DC up to V02 and to bring the DC back to V02. The date of the appointment for V02 will be confirmed.

If the timing of the telephone call should fall on a weekend or a holiday, the call should be made on the next business day. If contact is not made on the designated day, study staff will continue calling until contact is made. Every telephone attempt and its outcome will be documented in the source document.

[Table 9.1](#) and [Table 9.2](#) present, respectively, the injection site reactions and systemic reactions that are prelisted in the DCs and CRF, together with the intensity scales.

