**Table 9.1: Solicited injection site reactions : terminology, definitions, and intensity scales**

CRF term (MedDRA lowest level term [LLT])	Injection site pain	Injection site erythema	Injection site swelling	Upper limb edema	Extensive swelling of the vaccinated limb
Diary card term	Pain*	Redness*	Swelling*	Change in limb circumference*	Extensive limb swelling*
Definition		Presence of a redness including the approximate point of needle entry	Swelling at or near the injection site Swelling or edema is caused by a fluid infiltration in tissue or cavity and, depending on the space available for the fluid to disperse, swelling may be either soft (typically) or firm (less typical) to touch and thus can be best described by looking at the size of the swelling	Increase in limb circumference compared to pre-vaccination measurement of the same arm	Swelling of the injected limb including the adjacent joint (i.e., elbow and/or shoulder) as compared to baseline.
Intensity scale*	Grade 1: No interference with activity Grade 2: Some interference with activity Grade 3: Significant; prevents daily activity	Grade 1: $\geq 25$ to $\leq 50$ mm Grade 2: $\geq 51$ to $\leq 100$ mm Grade 3: $> 100$ mm	Grade 1: $\geq 25$ to $\leq 50$ mm Grade 2: $\geq 51$ to $\leq 100$ mm Grade 3: $> 100$ mm	Grade 1: $> 0$ to $< 25$ mm increase over pre-vaccination measurement Grade 2: $\geq 25$ to $< 50$ mm increase over pre-vaccination measurement Grade 3: $\geq 50$ mm increase over pre-vaccination measurement	Not applicable‡

\* If any Grade 3 solicited injection site reaction (including ELS) is present, the subject or subject's parent/guardian will be instructed to call the site immediately. See procedure in [Section 5.1.4](#).

† For the subjective reaction of pain, subjects or subject's parent/guardian will record the intensity level (Grade 1, 2, or 3) in the DC. For the measurable reactions of redness, limb circumference, and swelling, they will record just the size of the reaction, and the classification, as Grade 1, 2, or 3 will be assigned by the statistician.

‡ By convention, ELS is considered as severe.

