***Important notes for the accurate measurement of limb circumference:***

Study personnel will instruct the subject (or subject and their parent/guardian) how to perform and record the limb circumference measurements using the measuring tape and measuring horizontally at the level of the axilla. The subject will be requested, under the supervision of the study staff, to perform the baseline measurement of both arms with the staff, immediately before immunization (baseline measurement) at V01. The circumference of both arms will be recorded in the source document and that of the vaccinated arm will be transcribed in the subject's DC. The measurement of the vaccinated arm will be recorded daily by the subject or subject's parent/guardian in the DC.

If the subject develops Grade 3 change in limb circumference ( $\geq 50$  mm over pre-vaccination measurement at baseline) or ELSa (soft tissue swelling that occurs post-vaccination and extends from the injection site to involve an adjacent joint [e.g. the elbow, shoulder joint, or both]) which occur during the 7-day period after vaccination, the subject (or parent/guardian) is required to contact the site immediately. The site must attempt to arrange for the subject to be seen at the study site within 24 hours to assess the extent of the reaction. The subject (or parent/guardian) is to be instructed to take measurements of the vaccinated limb circumference and record in the DC until the swelling is resolved (See OG for details).

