4.4.1.1.7 Ongoing

Ongoing is derived from the last daily intensity of the solicited period computed as described in [Section 4.4.1.1.1](#) and the maximum intensity on the ongoing period. The investigator's ongoing flag is not used because the measurement would determine the ongoing status of the reaction. Note the intensity could be considered None (not a reaction) in the analysis despite being considered a reaction by the investigator (e.g., swelling measurement > 0 mm but < 25 mm in adults).

If the last daily intensity of the solicited period is at least Grade 1 and maximum intensity on the ongoing period is also at least Grade 1, then the reaction is considered ongoing. In any other cases the reaction will not be considered as ongoing.

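### The protocol gives two different triggers for continuing arm-circumference measurement until resolution, and the SAP separately classes a reaction present on D7 with no later record as not ongoing

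*Protocol*

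**What the plan says.** **Continued measurement.** Protocol 5.1.4, V01 step 16, has two relevant sentences. The first lists when the subject must contact the site and names the circumference change separately ("develop significant change in arm circumference (increased", with a 50 mm threshold). The second, on continued measurement, is narrower: "In cases of Grade 3 injection site swelling or ELS, the subject (or parent/guardian) is to be instructed to take measurements" of the vaccinated arm until resolution.

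The limb-circumference notes in Protocol 9.3.1.3.2 begin "If the subject develops Grade 3 change in limb circumference" (50 mm or more) or ELS, and conclude that the subject "is to be instructed to take measurements of the vaccinated limb circumference and record in the DC until the swelling is resolved". SAP 4.3.1.3.2 repeats these notes. Step 16 and both versions of the notes refer to the Operating Guidelines for details.

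**Grading.** Protocol Table 9.1 treats the two reactions as separate CRF terms. For injection site swelling the top grade is "Grade 3: $> 100$ mm". For upper limb edema it starts at 50 "mm increase over pre-vaccination measurement". ELS is a third term and has no size grade.

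**Recording period.** Step 14 asks for solicited reactions in the diary for D0 to D7. The opening of Section 9.3.1.3.2 has solicited items recorded "on the day of vaccination and for the next 7 days (i.e., D0 to D7) until resolution".

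**Ongoing status.** SAP 4.4.1.1.7 calls a reaction ongoing only if the last daily intensity of the solicited period and the maximum intensity afterwards are both at least Grade 1. It then adds: "In any other cases the reaction will not be considered as ongoing". The investigator's ongoing flag is not used. Under SAP 4.4.1.1.1 the later intensity comes from the record made after the solicited period.

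**The concern.** The two triggers cannot be loose names for one event, because Table 9.1 grades them on different measurements and step 16 itself names the circumference change separately before leaving it out of the measuring sentence. Whether a subject is told to keep measuring past D7 can therefore depend on which section the site works from.

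The SAP rule is a separate matter and would apply even if the protocol were consistent. Its reason for setting the investigator's flag aside is that the measurement decides the status. That reason fails when there is no measurement: absence of a record then gives the same result as a recorded resolution. Elsewhere the SAP keeps the two apart; SAP 4.4.1.1.3, for example, has a missing category for presence.

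At stake is the description of how long reactions last. Among the derived variables in SAP 4.4.1.1, ongoing status is the one that says whether a solicited reaction persisted past D7, and any miscoding from a missing record goes one way, towards not ongoing.

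**Working it through.** The plan gives no figure on this point to reproduce, so the check is one of logic.

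**Step 1: compare the triggers.** Inputs: step 16 applies if there is Grade 3 injection site swelling or ELS; Section 9.3.1.3.2 and SAP 4.3.1.3.2 apply if there is a Grade 3 circumference change or ELS. Three yes/no conditions give 2 × 2 × 2 = 8 combinations.

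| Grade 3 swelling | Grade 3 circumference | ELS | Step 16 | 9.3.1.3.2 / SAP | Agree? |
|---|---|---|---|---|---|
| no | no | no | no | no | yes |
| no | no | yes | yes | yes | yes |
| no | yes | no | no | yes | **no** |
| no | yes | yes | yes | yes | yes |
| yes | no | no | yes | no | **no** |
| yes | no | yes | yes | yes | yes |
| yes | yes | no | yes | yes | yes |
| yes | yes | yes | yes | yes | yes |

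They disagree in 2 of 8, and in no combination that includes ELS. Two subjects without ELS illustrate this:

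- A 55 mm circumference increase (Grade 3) with 60 mm of swelling (Grade 2) falls under Section 9.3.1.3.2 but not under step 16.
- 110 mm of swelling (Grade 3) with a 30 mm increase (Grade 2) falls under step 16 but not under Section 9.3.1.3.2.

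**Step 2: compare the recording periods.** Step 14 stops at D7. Section 9.3.1.3.2 names D0 to D7 and resolution in the same phrase. If the latter covers every solicited reaction, it also covers both example subjects, and the special triggers add little. If it does not, the gap in step 1 stands. The text does not settle which reading is meant.

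**Step 3: apply SAP 4.4.1.1.7.** The rule is: ongoing = (D7 intensity at least Grade 1) and (later maximum at least Grade 1); otherwise not ongoing.

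| D7 intensity | Later record | Derived status |
|---|---|---|
| Grade 1, 2 or 3 | Grade 1 or higher | ongoing |
| Grade 1, 2 or 3 | none (resolved) | not ongoing |
| Grade 1, 2 or 3 | missing | not ongoing |

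The last two rows cannot be told apart, even if the investigator marked the reaction as ongoing.

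**Step 4: scale.** The documents give no rate of Grade 3 circumference change. If it were 2% to 5% (an assumption), a cell of 75 subjects would hold 75 × 0.02 = 1.5 to 75 × 0.05 = 3.75 such subjects. Only those with no swelling above 100 mm and no ELS meet the conflicting triggers. Only those still at Grade 1 or higher on D7 with no later record are coded as in the last row. Neither fraction is given.

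**The case against.** The best case for leaving the text alone has several parts, and most of it stands as a limit on the consequence.

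- Neither trigger is worded as exclusive. A site that follows both sections would continue measurement in every case that either one names, and the general diary wording in Section 9.3.1.3.2 may cover the rest. The loss arises mainly at a site working from Section 5.1.4 alone, or when a record is simply missing.
- The Operating Guidelines may already resolve the matter. They are not among the documents, so this can be neither confirmed nor excluded.
- There are safeguards. An increase of 50 mm or more prompts contact and an attempted visit within 24 hours; the D8 call asks about unreported Grade 3 reactions; the diary is reviewed at V02; and Protocol 13.2 has missing diary data clarified verbally. These make a missing record less likely but do not change how one is coded.
- Grade 1 upper limb edema is any increase above 0 mm, so a new missing category could fill with trivial differences. This is a fair objection, and the fix has to allow for it.

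A reader might infer that unresolved Grade 3 edema will be reported as ended. The documents do not go that far. The SAP says not ongoing, SAP 5.3.1.5 leaves missing stop dates missing, and SAP 4.4.1.1.6 makes the overall number of days not applicable. SAP Table 5.1 names no ongoing-status output. It does list duration for solicited reactions, but nothing ties that to the ongoing rule.

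A reader might also infer that the ELS alert threshold is weakened. It is not: ELS is in both triggers, and the threshold (3% or more of recipients) counts occurrence, not persistence.

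**Conclusion.** The contradiction between step 16 and Section 9.3.1.3.2 (with its SAP copy) is real and confined to two combinations: Grade 3 circumference change alone and Grade 3 swelling alone. The difference between step 14 and Section 9.3.1.3.2 on the recording period is also real. Separately, the SAP rule does not distinguish a missing post-D7 record from resolution, so persistence past D7 can be understated. Whether it will be depends on how often that record is missing, which the documents do not say. That it is understated in every group is likewise not shown: the rule is the same for all groups, but no missing-record rates are given.

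The size is small. ELS occurrence, the ELS threshold, and D0 to D7 incidence, maximum grade, onset and days of occurrence do not depend on ongoing status. The study is descriptive and tests no hypotheses. The 2% to 5% rate is an assumption used only for scale. This is a worthwhile clarification that leaves the main safety results as they are.

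**What to change.** **Protocol, SAP and Operating Guidelines.** Reconcile Protocol 5.1.4 steps 14 and 16, both parts of Protocol 9.3.1.3.2 (the general diary instruction and the limb-circumference notes) and SAP 4.3.1.3.2, so that one instruction says which reactions are measured past D7 and for how long. Check the Operating Guidelines against it. Which trigger and which period apply is for the sponsor to decide.

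**SAP 4.4.1.1.7.** Add one case: if the last solicited-period intensity is Grade 1 or higher and no post-D7 intensity is recorded, ongoing status is missing. Report the number of such subjects by reaction, vaccine group and D7 grade, so that Grade 1 circumference differences of a few millimetres do not hide the Grade 3 cases.

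**Cost.** A few reconciled sentences and one line of derivation; the SAP change needs no new data. The drawback is that some subjects will have missing ongoing status, many of them possibly with only a Grade 1 circumference change.

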#### Telephone Call 1 (D8 + 3 Days)

**Note:** If D8 falls on a weekend or a holiday, the telephone call may be made on the following business day.

- 1) Record relevant information concerning the subject's health status on the telephone contact form. If an SAE, Grade 3 solicited adverse reaction (including ELS) has occurred, follow the instructions in [Section 10](#) for reporting it.
- 2) Remind the subject or subject's parent/guardian to do the following:
  - Continue to complete the DC, and bring it to V02.
  - Notify the site in case of an SAE.
- 3) Confirm V02 appointment.

#### V02 (window 30–44a days after V01): Collection of Safety Information and Blood Sample

- 1) Collect the DC. Review the pages of the DC with the subject or subject's parent/guardian, including any AEs, concomitant medications, or therapy and medical visits that occurred since vaccination.
- 2) Obtain the second blood sample (see [Section 7.1](#) for detailed instructions regarding the handling of blood samples).

---

a For subjects in the CMI subset, the V02 window will be between D30 and D37

- 3) Give the subject or subject's parent/guardian a memory aid (MA) and provide instructions for the MA completion. Inform them to expect the 6-month telephone follow-up.

#### Telephone Call 2 (D180 +14 days)

- 1) Review the MA with the subject or subject's parent/guardian.
- 2) Record relevant information concerning the subject's health status on the telephone contact form. If an SAE or MAAE occurred, follow the instructions in [Section 10](#) for reporting it.
- 3) Complete the relevant eCRF forms for this call, as well as the termination record in the eCRF.

#### ***SAEs and AEs That Are Related to Vaccination or That Led to Discontinuation:***

At any time during the study, a subject who experiences an SAE or an AE must be followed if *either* of the following is true:

- The SAE or AE is considered by the Investigator to be related to vaccination, and is not resolved by the end of the subject's participation in the trial
- The subject has been discontinued from the trial because of the SAE or AE

Any such subject must be followed until the condition resolves, becomes stable, or becomes chronic.

#### **5.1.5 Planned Trial Calendar**

The following dates are approximate. The actual dates may differ as, for example, the trial will not start until all the appropriate regulatory and ethical approvals have been obtained.

Planned trial period - FVFS (first visit, first subject) to LVLS (last visit, last subject):

Adult Subjects: October 2015–July 2016

Adolescent Subjects: April 2016–April 2017

Older Adult Subjects: May 2016–March 2017

Planned inclusion period - FVFS to FVLS (first visit, last subject):

Adult Subjects: October 2015–December 2015

Adolescent Subjects: April 2016–October 2016

Older Adult Subjects: May 2016–September 2016

Planned primary vaccination period: Please see dates for planned trial period

Planned end of triala: April 2017

Planned date of final clinical study report: November 2017

---

a End of trial is defined as the date of the last contact with a subject i.e. 6-month follow-up telephone call

[REDACTED]

[REDACTED]

[REDACTED]

- [REDACTED]
- [REDACTED]
- [REDACTED]
- [REDACTED]
- [REDACTED]

[REDACTED]

- [REDACTED]
- [REDACTED]

[REDACTED]

Study continuation will be determined pending final results of the ESDR and any potential investigation(s). If the risk for certain SP0173 formulation(s) has been determined as high, enrollment of the next age groups (adolescents and older adults) for the respective formulation will not proceed.

In addition to the ESDR, the usual and ongoing process of monitoring safety signals will continue unchanged (See [Section 3](#)).

Apart from the ESDR and the ongoing safety review, the study may be interrupted at any time if new data about the investigational product become available, and/or on advice of the Sponsor, the IEC/IRB, or the governing regulatory authorities in the US where the study is taking place.

If the study is prematurely terminated or suspended, the Sponsor will promptly inform the Investigators, the IECs/IRBs, and the regulatory authorities of the reason for termination or suspension. If the study is prematurely terminated for any reason, the Investigator will promptly inform the study subjects/subjects' parents/guardians and should assure appropriate therapy and follow-up.

## 5.2 Enrollment and Retention of Trial Population

### 5.2.1 Recruitment Procedures

Subjects may be recruited from the general population. The site will ensure that any advertisements used to recruit subjects (informational brochures, letters, pamphlets, posters, and other advertisements) are submitted to Sanofi Pasteur prior to submission to the IRB for approval.

### 5.2.2 Informed Consent Procedures

Informed consent is the process by which a subject (or an adolescent subject and their parent/guardian) voluntarily confirms his or her willingness to participate in a particular trial. Informed consent must be obtained before any study procedures are performed. The process is documented by means of a written, signed, and dated ICF.

For this study, in addition to the ICF that is signed by the subject's parent/guardian, subjects that have not reached the legal age of majority (according to state regulations) will be asked to review and sign a separate informed assent form.

In accordance with GCP, prior to signing and dating the consent and assent form, the subject (or the adolescent subject and their parent/guardian) must be informed by appropriate study personnel about all aspects of the trial that are relevant to making the decision to participate, and must have sufficient time and opportunity to ask any questions.

The actual ICF form used at each center may differ, depending on local regulations and IEC/IRB requirements. However, all versions must contain the standard information found in the sample ICF provided by the Sponsor. Any change to the content of the ICF must be approved by the Sponsor and the IEC/IRB prior to the form being used.

If new information becomes available that may be relevant to the subject's or the adolescent subject and their parent/guardian willingness to continue participation in the trial, this will be communicated to him/her in a timely manner. Such information will be provided via a revised ICF or an addendum to the original ICF.

Informed consent forms will be provided in duplicate, or a photocopy of the signed consent/assent will be made. The original will be kept by the Investigator, and the copy will be kept by the subject and/or subject's parent/guardian.

Documentation of the consent process should be recorded in the source documents.

In designated study sites, a convenience sample of 36 adolescents (10–18 years of age), 60 adults (19–64 years of age), and 60 older adults ( $\geq 65$  years) will be invited to provide an additional blood sample for CMI testing. An addendum to the ICF will be prepared to request voluntary provision of an additional blood sample (approximately 10 mL) for the test. Prior to signing and dating the addendum, the subject (or the adolescent subject and their parent/guardian) must be provided by appropriate study personnel with the relevant information for making the decision, and must have sufficient time and opportunity to ask any questions. A photocopy of the signed CMI addendum will be made and given to the subject.

